12.4 Analysis of the primary endpoint(s)

12.4.1 Definition of primary endpoint(s)

Incidence of ocular and non-ocular AEs are considered primary endpoints.

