12.4.2 Statistical model, hypothesis, and method of analysis

No formal hypothesis tests will be performed in this study. All safety analyses will be performed using the FAS.

Adverse events

The number (and percentage) of subjects with treatment-emergent adverse events (events started after the single dose of study treatment or events present prior to start of study treatment but which increased in severity based on preferred term) will be summarized in the following ways:

- by treatment, primary system organ class and preferred term
- by treatment, primary system organ class, preferred term and maximum severity
- by treatment, Standardized MedDRA Query (SMQ) and preferred term

Separate summaries will be provided for study treatment related adverse events, death, serious adverse events, other significant adverse events leading to discontinuation of the study. Separate presentations will be provided related to ocular events in the study eye and fellow eye and systemic events. Additional summaries will be provided by severity and causality (separately assessed for the injection procedure and the drug). Subject listings of all adverse events will be provided. Deaths and other serious or clinically significant non-fatal adverse events will be listed separately.

A subject with multiple adverse events within a primary system organ class is only counted once towards the total of the primary system organ class.

Ophthalmic examinations

Pre-injection and post-injection IOP measurements will be listed.

Vital signs

All vital signs data will be listed by subject and, if ranges are available, abnormalities will be flagged with thresholds representing clinical relevant abnormality.

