## **2.5 Analysis of the primary objective**

### **2.5.1 Primary endpoint**

The incidence of ocular and non-ocular AEs are the primary endpoints. The primary endpoints will be analyzed for the FAS.

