### **2.8.1 Adverse events**

AEs will be coded using MedDRA Version 21.1.

All AEs will be listed.

Summaries will include all treatment emergent AEs which are defined as AEs which start on or after the date of the injection of study treatment up until the patient discontinues or completes the study.

Analyses will be performed for ocular AEs for the study eye only and non-ocular AEs. Ocular and non-ocular AEs will be presented separately. Ocular AEs for the fellow eye will be listed only.

The number and percentage of subjects who reported treatment emergent AEs will be summarized by primary SOC and PT for:

- all AEs
- all AEs by maximum severity
- all AEs by investigator causality assessment (relationship to study treatment and/or study treatment administration procedure)
- AEs leading to study discontinuation
- all serious adverse events (SAE)

If a subject reports more than one AE with the same PT, the AE will be counted only once for that PT. If a subject reports more than one AE within the same primary SOC, the subject will be counted only once for that SOC.

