### **2.8.1.1 Adverse event reporting for CT.gov**

For the legal requirements of clinicaltrials.gov, two required tables on treatment emergent AEs which are not SAEs with an incidence greater than or equal to x% (default is 5% but a lower cut off may be applied and this will be determined based on the final data) and on treatment emergent SAEs will be provided by SOC and PT for the FAS.

If for the same subject, several consecutive AEs (irrespective of study treatment causality, seriousness and severity) occurred with the same SOC and PT:

- a single occurrence will be counted if there is  $\leq 1$  day gap between the end date of the preceding AE and the start date of the consecutive AE
- more than one occurrence will be counted if there is  $> 1$  day gap between the end date of the preceding AE and the start date of the consecutive AE

For occurrence, the presence of at least one SAE/non SAE has to be checked in a block e.g. among AE's in a  $\leq 1$  day gap block, if at least one SAE is occurring, then one occurrence is calculated for that SAE.

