## 4 Change to protocol specified analyses

Protocol section 12.2 states that relevant medical histories and current medical conditions at baseline will be summarized. Given the small sample size this data will be listed only.

Protocol section 12.3 states that descriptive statistics for exposure to study treatment and the cumulative number of injections will be presented. As subjects are only scheduled to receive a single injection of study treatment the total number of patients who received an injection will be presented.

Protocol section 12.3 states that concomitant medications and significant non-drug therapies prior to and after the start of the study treatment will be summarized. Given the small sample size this data will be listed only.

Protocol section 12.4.2 states that treatment emergent AEs will be summarized by SMQ and PT. This summary will not be produced, treatment emergent AEs will be presented by SOC and PT only.

Protocol section 12.4.2 states that AE presentations will be presented for the fellow eye. Adverse events for the fellow eye will be listed only.

Protocol section 12.4.2 states that pre-injection and post-injection IOP measurements will be listed. Instead, IOP measurements will only be listed for subjects who have at least IOP measurement meeting the criteria defined in SAP [Section 2.8.3.1](#).

Protocol section 12.4.2 states that all vital signs data will be listed. Instead, vital signs measurements will only be listed for subjects who have at least one vital signs measurement meeting the criteria defined in SAP [Section 2.8.3.2](#).

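### SAP 2.8.1 counts only study-eye and non-ocular events, so the ocular primary endpoint is tabulated more narrowly than defined and a serious fellow-eye event would be missing from the CSR SAE table

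*SAP*

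**What the plan says.** The endpoint names no eye. Protocol 12.4.1 reads "Incidence of ocular and non-ocular AEs are considered primary endpoints", and SAP 2.5.1 reads "The incidence of ocular and non-ocular AEs are the primary endpoints".

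For the analysis, protocol 12.4.2 plans by eye: "Separate presentations will be provided related to ocular events in the study eye and fellow eye and systemic events". SAP 2.5.2 sends the reader to SAP 2.8.1 for the AE analyses. There the scope is "Analyses will be performed for ocular AEs for the study eye only and non-ocular AEs", followed by "Ocular AEs for the fellow eye will be listed only". Five summaries by SOC and PT come after that statement: all events, events by maximum severity, events by causality, events leading to study discontinuation, and serious events. The same section also says "All AEs will be listed".

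SAP Section 4 records the departure: "Protocol section 12.4.2 states that AE presentations will be presented for the fellow eye. Adverse events for the fellow eye will be listed only". It gives no reason. SAP 2.8.1.1, on CT.gov reporting, says that tables on non-serious events and on "treatment emergent SAEs will be provided by SOC and PT for the FAS", and states no eye limit. SAP Section 1 says that the CT.gov analyses are not presented in the CSR.

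**The concern.** Safety is the only objective of this single-arm study and AE incidence is its only endpoint, so the AE tables are the result. Three things do not line up.

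- The ocular endpoint is defined for ocular events in general but tabulated for one eye. Neither SAP 1.2 nor SAP 2.5.1 was changed to say so.
- The SAE summary is described as covering all serious events but, under the scope set just before it, leaves out serious events in the fellow eye. A reader who takes the CSR SAE table as complete could be wrong. Likewise, a subject who left the study because of a fellow-eye event would count in the disposition summary (SAP 2.3.1) but not in the table of AEs leading to discontinuation.
- The registry SAE table may follow a different rule from the CSR SAE table, so the two could show different numbers of affected subjects with no explanation in the plan.

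**Working it through.** The documents give no power, event count or AE rate, so there is no figure to reproduce. The main check is one of scope.

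| Output | Study-eye ocular | Non-ocular | Fellow-eye ocular |
|---|---|---|---|
| Endpoint definition (protocol 12.4.1, SAP 2.5.1) | included | included | not excluded |
| Presentations planned in protocol 12.4.2 | yes | yes | yes |
| Five summaries in SAP 2.8.1 | counted | counted | not counted |
| AE listing (SAP 2.8.1) | listed | listed | listed |
| Deaths summary (SAP 2.8.2) | no eye limit | included | no eye limit |
| CT.gov tables (SAP 2.8.1.1) | counted | counted | not stated |

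The gap is in the third row, and the ambiguity is in the last. Section 2.8.1.1 sits beneath 2.8.1. If the limit carries down, the registry SAE table omits fellow-eye SAEs without saying so. If it does not, the registry can count a subject whom the CSR table omits.

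Size, as illustration. Input: N = 30 (approximate number to be injected, protocol Section 5 and SAP 1.1).

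1. Weight of one subject in a fellow-eye table: 1/30 = 3.3 percentage points. Exact (Clopper-Pearson) 95% interval for 1/30: 0.1% to 17.2%. For 0/30: 0% to 11.6%.
2. Chance that at least one subject has a fellow-eye event that no SAP 2.8.1 summary counts: 1 − (1 − p)^30, where p is an assumed proportion of subjects with such an event.

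| Assumed p | Expected subjects, 30p | Chance of at least one |
|---|---|---|
| 1% | 0.3 | 26% |
| 3% | 0.9 | 60% |
| 5% | 1.5 | 79% |
| 10% | 3.0 | 96% |

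These rates are for any fellow-eye event. Serious ones would be rarer, but the documents give no rate for them.

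3. Could the fellow eye serve as a formal comparator? In an exact McNemar test with all d discordant subjects in one direction, the two-sided p-value is 2 × 0.5^d. That gives 0.063 for d = 5 and 0.031 for d = 6, so at least six are needed. Power at N = 30, with eyes assumed independent, is about 3% for 10% against 3%, 25% for 20% against 5%, and 62% for 30% against 5% (all assumed rates). No such test is planned.

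**The case against.** The case for leaving the plan alone has weight. The change is declared in SAP Section 4, and its wording covers serious events because it covers all fellow-eye AEs. Every AE is listed, so with about 30 subjects and two visits a reader can count fellow-eye events by hand. A study-eye focus suits an objective about a drug delivered by prefilled syringe into that eye. Section 2.8.1 states its scope before naming the tables, so a table with that scope is correct for it.

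Most of this stands, and it rules out several stronger readings.

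- A reader might infer that fellow-eye events vanish from every table or are lost. They do not: they are listed, the deaths summary has no eye limit, and the CT.gov tables state none.
- A reader might treat the fellow eye as the trial's internal control. Neither document does. Protocol 6.2.1 allows that eye to be treated under clinical practice. The prior-treatment exclusions in protocol 5.2 for anti-VEGF injection, intraocular corticosteroids and surgery apply to the study eye only, and so does the nAMD inclusion criterion in 5.1. An injection of the fellow eye shortly before enrollment is therefore possible.
- A reader might infer that the reported ocular incidence is too low, for example 2/30 = 6.7% against 3/30 = 10.0% when one further subject has a fellow-eye event. The second figure pools both eyes. The protocol plans separate presentations, so the study-eye 6.7% would be right as it stands.

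What the objection does not answer is that the endpoint definition was left unrestricted, that the departure has no stated reason, and that the SAE summary is not complete. Section 4 cites small sample size for listing medical history and concomitant therapies, but says nothing of the kind for the fellow eye.

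**Conclusion.** The point holds as a gap in reporting scope. SAP 2.8.1 tabulates the ocular primary endpoint more narrowly than both documents define it and than protocol 12.4.2 planned, and the CSR SAE summary can omit a serious event that appears only in a listing. Whether CSR and registry SAE counts will agree cannot be settled from the plan.

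The effect is bounded. The study-eye incidence, the sample size and every stated figure are unchanged, and no error rate is involved because no test is planned. What is missing is a fellow-eye count in which each subject weighs 3.3 points. Under assumed rates of 1% to 10%, the chance that at least one subject goes uncounted is 26% to 96%. These figures rest on N = 30 and on rates that the documents do not supply. The conclusion on scope rests on the text alone. The change is worth making because it is cheap and restores what the protocol planned.

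**What to change.** Before database lock, amend the SAP as follows.

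- **2.8.1:** add a separate fellow-eye column or table by SOC and PT for treatment-emergent AEs and SAEs. Make the SAE summary count events in either eye.
- **2.8.1.1:** state that the CT.gov tables count events in both eyes.
- **Section 4:** remove the fellow-eye item, since the analysis would again match protocol 12.4.2.
- **Presentation:** label the fellow-eye results as descriptive and not as a control. Note that this eye may be treated during the study and that the eye-specific prior-treatment exclusions do not apply to it.

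If the sponsor prefers to keep the general AE tables to the study eye, the minimum is to say so where the endpoint is defined (SAP 1.2 and 2.5.1), give the reason in Section 4, count SAEs from either eye, and settle the scope of 2.8.1.1.

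The cost is SAP wording and one extra column or table. No new data are needed: AEs in either eye are already collected and due to be listed, and protocol 6.2.1 already requires fellow-eye treatment to be recorded in the eCRF.

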### **2.8.1.1 Adverse event reporting for CT.gov**

For the legal requirements of clinicaltrials.gov, two required tables on treatment emergent AEs which are not SAEs with an incidence greater than or equal to x% (default is 5% but a lower cut off may be applied and this will be determined based on the final data) and on treatment emergent SAEs will be provided by SOC and PT for the FAS.

If for the same subject, several consecutive AEs (irrespective of study treatment causality, seriousness and severity) occurred with the same SOC and PT:

- a single occurrence will be counted if there is  $\leq 1$  day gap between the end date of the preceding AE and the start date of the consecutive AE
- more than one occurrence will be counted if there is  $> 1$  day gap between the end date of the preceding AE and the start date of the consecutive AE

For occurrence, the presence of at least one SAE/non SAE has to be checked in a block e.g. among AE's in a  $\leq 1$  day gap block, if at least one SAE is occurring, then one occurrence is calculated for that SAE.

### **2.8.2 Deaths**

A summary of treatment emergent deaths will be presented by primary SOC and PT.

All deaths recorded in the clinical database will be listed.

### **2.8.3 Other safety data**

#### **2.8.3.1 Intraocular pressure (IOP) (mmHg)**

All IOP measurements will be listed for subjects who fulfil at least one of the following criteria:

- IOP  $> 30$  mmHg
- Increase  $\geq 10$  mmHg from pre-injection IOP to post-injection IOP within a visit

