8.4 Safety

Safety evaluation will include ocular and non-ocular assessments (eg vital signs, IOP, slitlamp and ophthalmoscopy) and will be performed according to the clinical practice. Any clinically significant changes should be reported as AEs.

For details on AE collection and reporting, refer to [Section 10.1.1](#).

The End of Study visit after 7 days (\pm 2) will be done at the site. The ocular assessments like slitlamp and ophthalmoscopy will be recorded in the source document and IOP will be entered in the eCRF. The non-ocular assessment (vital signs) will be recorded in the eCRF.

Additionally, a follow-up phone call 30 days after the End of Study Visit will be performed for subjects with any ongoing AEs at the End of Study Visit. Any occurred adverse events in this period should be collected in the source, and SAEs must be reported to Novartis safety according instructions in [Section 10.1.3](#).

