**Table 2-1 Clinically notable criteria for vital signs**

Variable	Category	Critical Values
Systolic blood pressure (mmHg)	High	Either $>180$ with an increase from baseline $>30$ or $>200$ absolute
	Low	Either $<90$ with a decrease from baseline $>30$ or $<75$ absolute
Diastolic blood pressure (mmHg)	High	Either $>105$ with an increase from baseline $>20$ or $>115$ absolute

Variable	Category	Critical Values
	Low	Either <50 with a decrease from baseline > 20 or <40 absolute
Pulse rate (bpm)	High	Either >120 with an increase from baseline of >25 or >130 absolute
	Low	Either <50 with a decrease from baseline >30 or <40 absolute

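### The SAP replaces the protocol's full IOP listing with one opened only by high-side triggers, so a low or falling IOP after injection cannot itself bring a subject into the listing

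*SAP*

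**What the plan says.** Protocol 12.4.2, under ophthalmic examinations, states: "Pre-injection and post-injection IOP measurements will be listed". It sets no cut-off and no direction.

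SAP 2.8.3.1 puts a filter in its place: "All IOP measurements will be listed for subjects who fulfil at least one of the following criteria". There are two criteria: an IOP above 30 mmHg, and an increase of 10 mmHg or more "from pre-injection IOP to post-injection IOP within a visit". There is no lower limit and no criterion for a decrease.

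SAP Section 4 declares the change: "Instead, IOP measurements will only be listed for subjects who have at least IOP measurement meeting the criteria defined in SAP" Section 2.8.3.1. It gives no reason. The entries for medical history and for concomitant medication in the same section do give one, the small sample size.

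Vital signs are also filtered, but in both directions. SAP Table 2-1 gives systolic pressure, diastolic pressure and pulse a High and a Low criterion each. The Low entry for diastolic pressure reads "Either <50 with a decrease from baseline > 20 or <40 absolute".

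On data capture, Protocol 8.4 says of the End of Study visit that "IOP will be entered in the eCRF", while slit lamp and ophthalmoscopy go to source only. Table 8-1 shows the same split at both visits.

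**The concern.** Safety is the trial's only objective, and the treatment is a single injection into the eye. Protocol 6.7.2 has the study eye checked before and after the injection for harm from the procedure or the drug, and that purpose is not confined to high pressure. The listing the protocol planned would show a fall as readily as a rise. The SAP's version shows a fall only when the same subject also has a high reading or a large rise.

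The SAP has no IOP summary table and no change-from-baseline output for IOP, so the filtered listing is the only place where IOP values are reported. At stake is whether a reader of the study report can see low post-injection pressures that the investigator did not report as AEs.

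**Working it through.** No sample size, power or error rate bears on this point. The check is a logical one on the listing rule.

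**Inputs**
- Criteria: SAP 2.8.3.1.
- Number of subjects: approximately 30 (Protocol 5; SAP 1.1).
- Readings per subject: assumed to be three, namely Day 1 pre-injection, Day 1 post-injection and Day 8. Table 8-1 marks IOP at Baseline and at End of Study. The SAP's within-visit criterion implies two readings on Day 1.

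**The rule.** A subject is listed if max(pre, post, Day 8) > 30, or if post − pre ≥ 10. The change criterion can operate only on Day 1, because the one injection is given there. A Day 8 value is therefore tested only against 30 mmHg.

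**Direction.** Lowering the post-injection or the Day 8 value can only lower the maximum or leave it unchanged, and the same is true of post − pre. So lowering either value can never move a subject from not listed to listed. Enumerating whole-number values from 0 to 60 mmHg for all three readings (61 × 61 × 61 = 226,981 profiles) gave 0 such switches.

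**Illustrative profiles** (assumed values, mmHg)

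| Pre | Post | Day 8 | Maximum | Post − pre | Listed? |
|---|---|---|---|---|---|
| 16 | 16 | 4 | 16 | 0 | No |
| 18 | 2 | 15 | 18 | −16 | No |
| 15 | 15 | 2 | 15 | 0 | No |
| 30 | 0 | 0 | 30 | −30 | No |
| 35 | 3 | 10 | 35 | −32 | Yes, through the pre-injection 35 |
| 15 | 3 | 32 | 32 | −12 | Yes, through the Day 8 value of 32 |

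In the first row the change from baseline at Day 8 is 4 − 16 = −12 mmHg. That row depends on the Day 1 post-injection value. Had it been 26, then 26 − 16 = 10 would meet the rise criterion, and all of the subject's values, including the 4, would be listed.

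**Length of a full listing.** 30 subjects × 3 readings = 90 study-eye rows. With only two readings per subject it is 30 × 2 = 60. If the fellow eye were listed as well, it is 90 × 2 = 180.

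**The case against.** The case for leaving the SAP as it stands has real content.

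- **No endpoint is touched.** The primary endpoints are the incidences of ocular and non-ocular AEs. IOP falls under other safety data, and even the protocol planned only a listing. This stands.
- **Important falls have another route.** Protocol 8.4 says "Any clinically significant changes should be reported as AEs", whatever the direction, and SAP 2.8.1 lists all AEs. This stands for falls that are judged clinically significant and reported. It does not cover the rest, which a measurement listing would show independently of that judgement.
- **Other checks exist.** Protocol 11.3 requires full verification of the data behind the primary variables, with access to source, where the slit-lamp and ophthalmoscopy records are kept. Concomitant medications and procedures are recorded and listed (Protocol 6.2.1; SAP 2.4.2), so a treated complication would leave a trace. A reader might infer that the IOP listing is the only data-based check on ocular AE reporting, or that a low-pressure problem could surface only through an AE report. The documents do not support either inference. These checks are partial, however, because none of them puts the low IOP value itself into the report.
- **The change is open and was reviewed.** Section 4 declares it, and the SAP document history shows the rise criterion made more sensitive before database lock, from 20 to 10 mmHg. So it is not an undisclosed departure from the protocol. Neither place gives a reason for leaving out the low side.
- **Nothing obliges IOP to mirror vital signs.** The only IOP cut-off in the protocol, exclusion criterion 2 at 25 mmHg, is also high-side, and no low cut-off appears anywhere. This is a fair argument against insisting on a low-side trigger. It does not count against listing every value, which needs no cut-off.

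**Conclusion.** The point holds as a reporting gap. With the SAP's two criteria, a low or falling post-injection IOP of any size cannot itself trigger the listing, and there is no other IOP output in which it would appear. IOP is the only post-injection ocular measurement in the clinical database, so low values not reported as AEs drop out of the reported IOP data.

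Its size is modest. It concerns one supportive listing in about 30 subjects. The values stay in the database, and the primary AE incidence does not change. The documents give no basis for estimating how many subjects would be affected, and the number could be none.

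A reader might also infer that any large fall, such as 16 to 4 mmHg by Day 8, is always hidden. That is too strong: such a subject is listed if the Day 1 post-injection reading is 26 mmHg or more, or if any reading exceeds 30.

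The conclusion rests on applying the 30 mmHg criterion to any of a subject's readings, and on counting Day 8 among the post-injection measurements in Protocol 12.4.2. The second reading agrees with the SAP's definition of post-baseline in 2.1.1.3.

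**What to change.** In SAP 2.8.3.1, restore the protocol's listing: all pre-injection, post-injection and Day 8 IOP values for the Full Analysis Set. Keep the two present criteria as flags on that listing, not as conditions for entering it. Delete the IOP entry in SAP Section 4, since the analysis would again follow the protocol.

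The cost is a slightly longer listing. The data are already in the eCRF. No protocol amendment, extra procedure or extra subject is needed. A full listing also avoids choosing a low-side cut-off, for which the documents give no basis, and it shows Day 8 rises that stay at or below 30 mmHg, which the within-visit criterion does not reach.

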6.1.3 Treatment duration

One injection of brolucizumab 6 mg PFS per subject will be administered at Baseline, with one End of Study follow up visit after 7 days (\pm 2 days).

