**Document History – Changes compared to previous final version of SAP**

Date	Time point	Reason for update	Outcome of update	Section and title impacted (Current)
9 Aug 2019	Prior to DBL	Data is coded with MedDRA V21.1	References to “most recent version at the time of DBL” changed to reflect Version 21.1 is used	S2.3.2 Subject demographics and baseline characteristics S2.4.2 Prior, concomitant and post therapies S2.8.1 Adverse events
9 Aug 2019	Prior to DBL	Sites have entered events prior to IFC on the eCRF	Text updated to reflect prior non-drug therapies and procedures are included in the listing	S2.4.2 Prior, concomitant and post therapies
9 Aug 2019	Prior to DBL	Criteria changed from increase $\geq$ 20 mmHg from pre-injection IOP to post-injection IOP within a visit to an increase $\geq$ 10 mmHg	Text stating the criteria is updated	Section 2.8.3.1 Intraocular pressure (IOP) (mmHg)
9 Aug 2019	Prior to DBL	Imputation of partial dates for medications is not required for any analyses	Section 5.1.2 removed	S5.1.2 Concomitant medication date imputation

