### **2.1.1.2 Baseline definition**

Baseline is defined as the last measurement/value before the injection of study treatment.

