### **2.1.1.3 Post-baseline definition**

Post-baseline measurements are defined as assessments after the injection of study treatment.

When change from baseline is of interest the following formula will be used for each scheduled visit where baseline and post-baseline values are both available:

Change from baseline = post-baseline value – baseline value

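### The IOP rise criterion in SAP 2.8.3.1 works only within a visit, so a Day 8 rise of 10 mmHg or more that ends at or below 30 mmHg does not trigger the IOP listing

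*SAP*

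**What the plan says.** Protocol 12.4.2 (Ophthalmic examinations) plans an IOP listing with no threshold: "Pre-injection and post-injection IOP measurements will be listed". It does not name Day 8.

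SAP 2.8.3.1 narrows this. All IOP values are listed, but only for subjects who meet at least one of two criteria: any IOP above 30 mmHg, or a rise of 10 mmHg or more "from pre-injection IOP to post-injection IOP within a visit". SAP 4 declares the change: "IOP measurements will only be listed for subjects who have at least IOP measurement meeting the criteria". The SAP plans no other IOP table or listing.

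Protocol 6.1.3 fixes the treatment: "One injection of brolucizumab 6 mg PFS per subject will be administered at Baseline". Protocol Table 8-1 schedules IOP at Baseline and again at the End of Study visit on Day 8, and protocol 8.4 says of that later visit that "IOP will be entered in the eCRF". Slit-lamp and ophthalmoscopy findings stay in the source documents.

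The SAP already has the terms needed to describe a later change. Section 2.1.1.2 states: "Baseline is defined as the last measurement/value before the injection of study treatment". Section 2.1.1.3 states: "Post-baseline measurements are defined as assessments after the injection of study treatment". The vital signs criteria in SAP Table 2-1 use change from baseline. The IOP criteria do not.

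**The concern.** A rise measured from before to after the injection, inside one visit, needs an injection at that visit. Day 8 has none. The relative criterion is therefore inoperative at the only scheduled visit after the injection day, and only the absolute limit of 30 mmHg remains.

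Safety is the study's sole objective, and IOP is the one ocular examination whose Day 8 result enters the clinical database. Under the present rule, a short-lived rise on the injection day brings a subject into the listing. A rise of the same size or larger, seen a week later and ending at or below 30 mmHg, does not. The report would then be silent on such a subject unless the investigator had recorded an adverse event.

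**Working it through.** The plan gives no IOP distribution and no expected count, so there is no figure to reproduce. The check is of the rule's logic.

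**Inputs**
- One injection, at Baseline (protocol 6.1.3).
- IOP scheduled at Baseline and Day 8 (protocol Table 8-1).
- Listing criteria: any IOP > 30 mmHg, or a within-visit rise ≥ 10 mmHg (SAP 2.8.3.1).
- Assumption: one reading before injection (p), one after injection on Day 1 (q) and one at Day 8 (d), in whole mmHg. The documents do not state the number of readings per visit.

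**Rule**

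A subject is listed if max(p, q, d) > 30 or q − p ≥ 10. The difference d − p does not enter.

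**Unlisted region for a Day 8 rise of 10 mmHg or more**

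1. A Day 8 rise of at least 10 requires d ≥ p + 10.
2. Not exceeding the absolute limit requires d ≤ 30.
3. Together, p + 10 ≤ d ≤ 30, which is possible only if p ≤ 20.
4. The Day 1 rise must be below 10, so q ≤ p + 9 ≤ 29. Day 1 then cannot trigger the absolute limit either.
5. The number of whole-mmHg Day 8 values that escape is 30 − (p + 10) + 1 = 21 − p.

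| p (mmHg, illustrative) | Unlisted Day 8 values | Unlisted rises | Count, 21 − p |
|---|---|---|---|
| 10 | 20 to 30 | 10 to 20 | 11 |
| 14 | 24 to 30 | 10 to 16 | 7 |
| 18 | 28 to 30 | 10 to 12 | 3 |
| 20 | 30 | 10 | 1 |
| 21 | none (21 + 10 = 31 > 30) | none | 0 |

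From 21 mmHg upward, any 10 mmHg rise exceeds 30 and is listed.

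**Illustrative subjects (p / q / d)**
- 14/16/26: Day 1 rise 16 − 14 = 2, maximum 26. Not listed, although Day 8 is 26 − 14 = 12 above the pre-injection value.
- 14/24/15: Day 1 rise 24 − 14 = 10. Listed, although Day 8 is only 15 − 14 = 1 above.
- 14/26/26: Day 1 rise 26 − 14 = 12. Listed, and the Day 8 value is shown because all of a listed subject's values appear.
- 14/16/31: maximum 31 > 30. Listed through Day 8 alone.

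**Comparison inside the SAP**

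In Table 2-1, a systolic pressure above 180 mmHg with an increase from baseline above 30 mmHg is notable. Vital signs are recorded at both visits, so that relative criterion can operate at Day 8. The IOP rise criterion cannot.

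**The case against.** The strongest reply is that this is a disclosed choice and a coherent one. In a study of a single prefilled-syringe injection, comparing IOP just before and just after the injection is a sensible target. SAP 4 announces the filter, and no two passages conflict. Protocol 8.4 requires changes of clinical significance to be reported as adverse events and counts IOP among the safety assessments. SAP 2.8.1 lists every adverse event. A Day 8 value above 30 mmHg still triggers the listing, and a subject listed for any reason has the Day 8 value shown.

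Most of this stands, and it limits the consequence. It does not remove the gap, because the adverse event route depends on the investigator's judgement of significance. What the listing would add is the Day 8 rise that was not judged significant.

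A reader might infer more than the documents support:
- *That the SAP departs silently from the protocol.* It does not, since SAP 4 states the change.
- *That the protocol promised a Day 8 listing.* Protocol 12.4.2 does not name Day 8.
- *That Day 8 IOP is never shown.* It is shown for every listed subject.
- *That the 10 mmHg cut-off affects Day 1 readings only.* The cut-off decides which subjects are listed, so it also decides whether their Day 8 values appear, as 14/26/26 shows.
- *That a 10 mmHg rise at Day 8 is a defined safety signal.* The SAP sets that figure for the within-visit comparison only. It serves here as a yardstick.

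**Conclusion.** The point holds as a gap in what triggers one supportive listing. A Day 8 rise of 10 mmHg or more goes unlisted when the pre-injection IOP is 20 mmHg or lower, the Day 1 rise is below 10 mmHg and the Day 8 value is 30 mmHg or lower. The wording logic is certain. How often it matters is not: the documents give no IOP distribution, so the number affected among about 30 subjects is unknown and may be zero.

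Adverse event incidence, the primary endpoint, is unchanged, and the Day 8 values remain in the database. The point therefore does not support a claim that the safety analysis is invalid. It is a low-priority improvement to the completeness of the safety output, worth considering because it costs so little.

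**What to change.** In SAP 2.8.3.1, replace the filtered listing with an unfiltered one: all IOP measurements in the clinical database, for every FAS subject, identified by eye, visit and timing relative to the injection. This covers the readings foreseen in protocol 12.4.2 and adds the Day 8 values held in the eCRF. Naming Day 8 goes a step beyond restoring the protocol text, so revise SAP 4 to say so.

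This needs no Day 8 cut-off. Rewording the rise criterion as a change from baseline would also close the gap, and the definitions exist in SAP 2.1.1.2 and 2.1.1.3. It would, however, apply at Day 8 a threshold that the documents do not set there, so the unfiltered listing is preferable.

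The cost is a somewhat longer listing: 30 subjects × 3 readings = 90 values for the study eye alone, or 90 × 2 = 180 if both eyes are recorded. Both figures rest on assumptions, because the documents state neither the number of readings per visit nor which eyes are measured. No new data collection is needed.
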